### **Mapping of unscheduled or early termination visits**

When visit assessments are missing, repeat assessments may be mapped to the appropriate visit in the database by the DM vendor, when appropriate. For these unscheduled assessments following a missing protocol visit or assessment, mapping will be done to the (closest) protocol visit at which the applicable assessment should have been performed before the date of unscheduled visit.

In case of a repeated or additional assessments for non-missing assessments, mapping will only be done for replacement if this is clearly agreed (at patient and visit level) with the client and specified by DM vendor (e.g. because it replaces an erroneous measure collected at the actual visit), and as such will be used in statistical data presentations. These agreements will be documented by the Sponsor as appropriate.

The data of early withdrawal may be mapped to the most appropriate scheduled post-baseline visit as applicable per assessment, to be agreed together with the DM vendor and the client on occurrence. The documentation of these agreements is to be finalized by the Sponsor as appropriate. For early termination visits in general mapping will be done to the closest protocol visit at which the applicable assessment should be performed after the date of early termination.

### **5.3 Interim analysis**

Not applicable.

### **5.4 Baseline characteristics**

#### **5.4.1 Inclusion/exclusion criteria**

Not applicable / not in the scope of this SAP following early termination of the study.

#### **5.4.2 Demographics**

Descriptive tabulations of the data for demographics and ADORE baseline characteristics will be made for the SAFe. Demographic data (including weight and height measurements) per treatment group and overall will be presented. Appropriate descriptive statistics for age, height, weight, BMI, race, ethnicity and gender will be given, including ALS history data, using data from ADORE baseline. Descriptive statistics will be n, arithmetic mean, SD, median, minimum and maximum for quantitative data. For qualitative data, frequency counts and percentages will be determined.

#### **5.4.3 Disposition**

To present disposition, summaries will be provided for all randomized, enrolled in extension, treated in extension, and completed extensions along with reasons for early discontinuation. Completion status will be derived from CRF form “Study Completion”. Additionally, the number/percentage of patients in the mITT and SAFe will be presented. The patient disposition will be presented per treatment group and overall.

#### **5.4.4 Medical history and Concomitant Medication**

Not applicable / not in the scope of this SAP following early termination of the study.

#### **5.4.5 Other screening data**

Not applicable following early termination of the study.

### **5.5 Statistical analysis primary and secondary efficacy endpoints**

All efficacy analysis will be conducted on the mITT set, unless otherwise specified.

#### **5.5.1 Primary analysis**

Not applicable, no primary endpoint for efficacy is included in this study.

#### **5.5.2 Secondary analysis**

##### **5.5.2.1 Overall Survival and ‘Survival Time’**

Time to event endpoints for overall survival and survival time definitions are reported in Section 4.2. Patients who early terminated the ADOREXT study for reasons different from death will be considered as still alive and with no respiratory insufficiency event at the time of study discontinuation, unless otherwise specified in the survival follow-up CRF form. Endpoints will be derived by combining the survival data from ADORE and ADOREXT.

Descriptive statistics including median, Q1/Q3 quartiles with 95% confidence intervals will be tabulated. Endpoints will be also summarized with the use of the Kaplan-Meier method.

The difference between the groups randomized in ADORE to FAB122 and placebo will be evaluated descriptively by means of a stratified log rank test. Hazard ratios and 95% confidence intervals will be estimated with the use of a stratified Cox proportional-hazards regression model with treatment group as the sole explanatory variable.

The difference between the groups will also be assessed using restricted mean survival time (RMST) analysis. Considering the duration of the ADOREXT study, the RMST will be performed up to the largest observation time from the pooled ADORE and ADOREXT data, adjusting for the stratification variables.

Randomization strata from ADORE study will be used for the stratified analysis. No adjustment will be performed for the treatment cross over following enrollment in ADOREXT study.

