#### 6.4. Phone contacts

Patients not willing to receive or continue receiving active treatment in the extension study or that had already discontinued study treatment during the course of the main ADORE study for safety reasons, will be asked to be contacted by phone every three months and followed up for vital status. These patients will not undergo the baseline assessments or any other study procedures.

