#### 11.3.4. Efficacy Analysis

Descriptive statistics (median, and the 25th and 75th percentiles with 95% confidence intervals) and Kaplan-Meier curves will be provided for patients participating in the extension study and patients that consented to only follow their vital status.

The primary aim of the analysis is to evaluate the difference between patients originally randomized to FAB122 versus those originally randomized to placebo using the extended follow-up data from the open-label phase. The difference in overall survival between patients originally randomized to FAB122 versus those originally randomized to placebo will be evaluated using a log-rank test, stratified for randomization factors. The effect of treatment will be expressed as hazard ratio. In case of non-proportional hazards, we will estimate the difference in restricted mean survival time (RMST).

---

In addition, we will explore the effect of treatment switching in the placebo arm using a rank preserving structural failure time model (RPSFTM) and inverse probability of censoring weights (IPCW). Details of the analyses will be provided in the SAP.

Changes in the in ALSFRS-R score, SVC, ALSAQ-40, EQ-5D-5L, and VAS score over time will be presented descriptively.

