## **6 CHANGES FROM PROTOCOL AND OTHER RELEVANT REMARKS**

Due to study early termination, some analysis planned in the protocol will not be performed. This SAP focuses on a subset of analyses related to objectives of safety, overall survival, and

disease progression. In particular, analysis will be performed for the primary endpoint, the overall survival and survival time. The ALSFRS-R score will also be described.

Overall survival and survival time endpoints definition will be updated to align with ADORE study. ALSFRS-R is also added to the secondary endpoints as it will be analyzed without mortality adjustment.

The mITT analysis set was not originally planned in the study protocol and included in the SAP to perform survival analysis combining ADORE and ADOREXT data.

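### SAP 5.5.2.1 runs RMST to the last pooled follow-up time, where one arm usually has nobody at risk, and names no stratum-adjusted estimator or tail rule (low priority)

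*SAP*

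**What the plan says.** SAP 5.5.2.1 compares the arms as randomised in ADORE, on ADORE and ADOREXT data combined, for overall survival and for survival time. It calls the comparison descriptive and names a stratified log-rank test and a stratified Cox model. For the third method it says only that "the RMST will be performed up to the largest observation time from the pooled ADORE and ADOREXT data, adjusting for the stratification variables". The strata are those of the ADORE randomisation; neither document lists them.

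Time runs from the first ADORE dose (SAP 4.2). Patients who leave ADOREXT for a reason other than death count as alive and "with no respiratory insufficiency event at the time of study discontinuation, unless otherwise specified in the survival follow-up CRF form". Under Protocol 6.4, patients off treatment "will be asked to be contacted by phone every three months and followed up for vital status", so some follow-up continues after treatment stops.

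For RMST there is no estimator, variance method, minimum number at risk, or rule for an arm whose follow-up ends before the horizon. SAP 6 adds nothing on this, SAP 8.3 names only SAS 9.4, and SAP 9.3 gives only table titles. In Tables 14.2.1.3 and 14.2.2.3, RMST is the only method named in the title. Protocol 11.3.4 brings RMST in only if hazards are non-proportional, gives no horizon or estimator, and leaves analysis details to the SAP.

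**The concern.** RMST is the area under the survival curve up to a horizon tau, so both curves must be defined that far. With staggered entry and a common end of study, the longest follow-up in the pooled data normally belongs to an early entrant who was still event-free when last seen. That patient is in one arm. The other arm's longest follow-up is usually shorter and also censored, so between that point and tau its Kaplan-Meier curve has no defined value. Stratum adjustment can multiply the problem: curves estimated by stratum and arm each end at their own, often earlier, time.

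What is at stake is reproducibility. Two programmers who both follow SAP 5.5.2.1 can report different adjusted differences from the same data.

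**Working it through.** 1. **No figure to reproduce.** The documents give no numerical tau, event count, power or alpha for this analysis, so the check is by formula and simulation.

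2. **Inputs from the documents.** About 300 patients in ADORE and 200–225 expected in ADOREXT (SAP 2.4), which is 200/300 = 67% to 225/300 = 75% roll-over (about 71% used). Main-study follow-up is 48 to 72 weeks (Protocol 2.1).

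3. **Assumptions, not in the documents.**
   - Set A: allocation 1:1 or 2:1; annual hazard 0.15, 0.20 or 0.30; entry over 60 weeks; cut-off 26 weeks after the last ADORE visit; close-out spread over 6 weeks; 10% per year extension drop-out; 4 strata; phone follow-up in 0, 50 or 100% of patients off treatment. Sensitivity runs varied these and added 2 or 8 strata and a thin tail (few early entrants).
   - Set B, coded separately: annual event risk 15–35%, accrual over 200–550 days, cut-off at day 1100.

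4. **Formula.** `RMST(tau) = integral of S(t) from 0 to tau`. If the shorter arm's last time m is censored, its area from m to tau is `(tau - m) x S(m)` with the tail held flat and 0 with the tail dropped. The longer arm is unaffected, so the arm-wise difference moves by `(tau - m) x S(m)`. With stratum weights w_k, the shift is the w_k-weighted sum of the same term over strata, one arm minus the other.

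5. **Support at the SAP's tau.**
   - Last observation censored: 99–100% of runs in A; everyone at risk at tau censored in 98–100% in B.
   - Patients at risk in total: median 1 (A and B), 2 with a thin tail; exactly one in 77–96% of runs in B. Thirty days earlier, 7–10 (A).
   - One arm with nobody at risk: 96–98% in A. In B the shorter arm ended on a censored time in 89–97%.
   - The A figures cover all three levels of phone follow-up.

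6. **Size of the tail effect.** In B the median gap tau − m was 3–21 days. Both extremes had 25% annual risk, so S is about 0.75^(1098/365.25) = 0.42 and 0.75^(1074/365.25) = 0.43. The arm-wise shift is then about 3 × 0.42 = 1.3 days to 21 × 0.43 = 9 days. Simulated medians in A:

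| Estimator | Held versus dropped, SAP's tau | Same, 10%-at-risk time |
|---|---|---|
| Arm-wise curves | 5–7 days (17–21 thin tail) | 0 |
| Stratum-by-arm curves | 5–11 days (4 strata), 8–15 (8 strata), 14–27 (thin tail) | 0–5 days |

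   Against a horizon of about 138 weeks (966 days), 5–15 days is 5/966 = 0.5% to 15/966 = 1.6%. Against an SD of 4.8–5.9 weeks (34–41 days), it is about 5/41 = 12% to 15/34 = 44% of one SD.

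7. **Does the horizon damage the comparison?** Pseudo-value regression in A:

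| | SAP's tau | 10%-at-risk time |
|---|---|---|
| SD of difference | 4.8–5.9 weeks | 4.1–5.1 weeks |
| SD / horizon (about 138 and 125 weeks) | 0.035–0.043 | 0.033–0.041 |
| 95% CI excludes 0 at HR 1 | 3–7% | 4–7% |
| Difference / SD at HR 0.75 | 1.05–1.48 | 1.03–1.45 |

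   Moving tau only to the smaller arm maximum changes the difference by a median 0.3–0.6 days (1.6–2.6 with a thin tail). In further runs, also on assumed inputs, Kaplan-Meier and stratum-weighted areas rejected in 4–7% at HR 1 at either tau. At HR 0.75 they rejected in 28–29% at the SAP's tau and 23–24% at the 10% time.

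**The case against.** The strongest reply is that little harm is shown. With ordinary estimators the SAP's horizon gives a correct false-positive rate and, if anything, slightly more power than a shorter one. The rule is pre-specified, is tied to the length of ADOREXT, and needs no treatment codes. The stakes are low: SAP 5.5.1 states "Not applicable, no primary endpoint for efficacy is included in this study", and SAP 6 explains that "Due to study early termination, some analysis planned in the protocol will not be performed". All of this stands, and it sets the priority. It is also fair that no document says a single patient will be at risk at tau. That is an inference, and in some runs there was more than one.

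The reply does not supply the missing rule. A horizon at which one arm usually has no data requires a tail convention, a required adjustment requires an estimator, and the SAP gives neither.

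A reader might go further and infer that results could differ by weeks. That would follow if the adjustment were made by censoring-weighted regression: in set A its SD at the SAP's tau was 22–32 weeks or 10–15 weeks, depending on whether a patient censored at tau counts as observed. The documents do not support this reading. The SAP does not mention that method for RMST. The only censoring weights planned, in Protocol 11.3.4, were for treatment switching, and SAP 5.5.2.1 drops that: "No adjustment will be performed for the treatment cross over following enrollment in ADOREXT study". A reader might also infer that the horizon invalidates the survival comparison. The false-positive rates and signal-to-noise ratios above do not bear that out.

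**Conclusion.** The point holds at low priority. The stated horizon is poorly supported: nearly always a censored time, usually with one patient at risk and one arm empty. The stratum-adjusted RMST difference therefore depends on an unstated tail convention, by a median of roughly 5–15 days under the assumed inputs and up to 27 with a thin tail. Inference from Kaplan-Meier areas or pseudo-values is essentially unaffected, and the log-rank and Cox results do not use tau.

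The direction and ordering of these results are more secure than the sizes, because the documents do not give allocation ratio, strata, event rates or actual follow-up. Confidence is medium.

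**What to change.** Replace the RMST sentence in SAP 5.5.2.1 with:

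> RMST will be computed up to the latest time at which at least 10% of each randomised arm remains at risk (and never beyond the smaller of the two arms' largest observation times); the adjusted difference will be estimated by regression of pseudo-values, computed from the pooled sample, on treatment and the ADORE randomisation strata as categorical terms, with robust standard errors.

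No new data are needed. At the 10% time a median of 10–21 patients per arm are at risk in the simulations. The costs, under the same assumptions:
- The horizon is a median 11–15 weeks shorter, or about 24 with a thin tail.
- A median of 0–1 deaths out of 72–131 (95th percentile 2–3) fall after tau and count only in the log-rank and Cox analyses.
- Power may be slightly lower.
- The 10% threshold is a convention.
- Tau now needs the treatment codes, so the rule must be fixed before lock and the value computed afterwards.

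SAP 1.0 is final (19 Apr 2024), and the documents do not say whether the database has been locked. If it has, report this as a supplementary analysis alongside the SAP's version.

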##### **5.5.2.2 ALSFRS-R questionnaire**

Descriptive statistics for absolute and change from extension baseline in total ALSFRS-R score will be presented by treatment group in summary tables.

Results will also be presented for the following subscales:

- Bulbar function (questions 1-3 of the ALSFRS-R)
- Fine motor function (questions 4-6 of the ALSFRS-R)

- Gross motor function (questions 7-9 of the ALSFRS-R)
- Respiratory function (questions 10-12 of the ALSFRS-R)

Only patients included in the mITT will be included in the summaries.

### **5.5.3 Other efficacy endpoints and examinations**

Not applicable / not in the scope of this SAP following early termination of the study.

## **5.6 Safety and tolerability evaluation**

All safety presentations will be created using the SAFe population.

### **5.6.1 Adverse events**

A treatment emergent adverse event (TEAE) is defined as an adverse event that appears at or after first dosing of extension. In case of (partially) missing start/stop dates, refer to Section [5.2](#).

An AE overview table will be created displaying the number of patients (and percentage) experiencing a treatment-emergent adverse event (TEAE) and the number of TEAEs for: any TEAE, any mild/moderate/severe TEAE, any unrelated/related TEAE, any serious AE, any serious TEAE, and any TEAE leading to study treatment discontinuation, any AE leading to death.

All TEAEs and those leading to death will be tabulated. SUSARs will be reported by the pharmacovigilance vendor.

All TEAEs are tabulated by System Organ Class (SOC) and Preferred Terms (PTs) within each SOC according to the MedDRA terminology list. TEAEs will be tabulated using frequency counts (number of patients with at least one event, and number of events) and percentage of patients with the event. Similar tables will be created for TEAEs leading to premature treatment discontinuation and Serious TEAEs. These summary tables will be presented by decreasing frequency of occurrence based on SOC and PT.

For summary tables, an AE is considered related if the causality to the study medication is classified as either ‘Probably Related’ or ‘Possibly Related’, where a missing relationship is also considered related. Otherwise, it will be considered unrelated for summary tables.

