### Rationale for the Current Study

As ALS is a rapidly progressive and fatal disease, this study is designed as an open-label extension (OLE) study to provide longer term access to daily oral edaravone to patients who have demonstrated a good tolerance in the ADORE trial (either FAB122 or placebo arm) during 48 weeks and up to 72 weeks.

The good tolerance for each patient who could be included in the current OLE study will be evaluated by the investigator, according to the individual favourable benefit/risk ratio which will be based on the available data.

This OLE study will also assess longer term safety, survival and therapeutic potential of daily oral edaravone.

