### **5.3. Exclusion Criteria**

Patients who meet any of the following criteria, will not be eligible for the study:

1. Patient who has a medical condition (e.g. cardiac, pulmonary, gastrointestinal, musculoskeletal, or psychiatric illness) or personal circumstances which, in the opinion of the investigator, will make initiation or continuation of treatment with FAB122 not tolerable for them from a risk and benefit point of view.
2. Patient who discontinued study drug prematurely in the double-blind phase of the study (ADORE Study) for safety reasons.
3. Patient who has received any other investigational drug within the period between last visit of the main study and first visit of the extension study (i.e. another trial, managed access program, open label extension or early access program)
4. History of known hypersensitivity to edaravone or to any of the excipients.

For patients who do not take FAB122 but are only followed up by phone, only inclusion criteria #1 and #5 will apply.

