### 9.1. Definitions

#### 9.1.1. Adverse Event

An AE is any unfavorable and unintended sign (including an abnormal laboratory finding), symptom, or disease temporally associated with the use of a medicinal (investigational) product, whether or not related to the medicinal (investigational) product. An AE is any symptom, sign, illness, or experience that develops or worsens in severity during the course of the study. Adverse events reported after consent but before the first dose of study drug are still to be documented by the investigator but will be considered non-treatment-emergent AEs.

Intercurrent illnesses or injuries should be regarded as AEs. Abnormal results of laboratory tests or diagnostic procedures are considered to be AEs if the abnormality:

- Is associated with clinical signs or symptoms.
- Is considered by the investigator to be of clinical significance.
- Results in study withdrawal.
- Fulfills any of the criteria for a SAE, as described in this section.
- Requires intervention or further evaluation to determine the etiology of the abnormality and/or assess the risk to the subject.
- Requires treatment.

Changes in ALS symptoms will not be documented as AEs unless they are extraordinary and/or unexpected.

A treatment-emergent adverse event (TEAE) is defined as an adverse event observed after the first dose of study drug. If a subject experiences an event both prior to and after starting study drug administration, the event will be considered a TEAE (of the treatment) only if it has worsened in severity (i.e., it is reported with a new start date) after study drug administration of the specific treatment, and prior to the start of another treatment, if any.

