### 11.3. Description of Statistical Methods

#### 11.3.1. Analysis Populations

Safety Analysis Set: The safety analysis set will consist of all subjects who receive at least 1 dose of IMP in the extension study.

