#### 3.1.2 Safety Analysis Set Extension (SAFe)

The SAFe population includes all patients enrolled in ADOREXT who have received at least one dose of the investigational drug during the extension study, irrespective of satisfying other criteria. This population will be used for the analysis of safety and tolerability, and statistical analysis will be done “as treated”. Although all patients will be treated with FAB122 in ADOREXT, data will be presented also using the randomization groups of ADORE study.

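### Extension-only TEAE tables are a coherent choice, but as the sole safety analysis they leave AEs unrelated to time on FAB122, which is what the long-term safety objective asks about

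*SAP*

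**What the plan says.** **Time zero.** SAP 5.6.1 counts as treatment-emergent "an adverse event that appears at or after first dosing of extension". Protocol 9.1.1 is less specific: "A treatment-emergent adverse event (TEAE) is defined as an adverse event observed after the first dose of study drug", without naming the study. It adds that an event present before dosing counts "only if it has worsened in severity (i.e., it is reported with a new start date) after study drug administration of the specific treatment". SAP 5.6.1 does not repeat that clause, and SAP 5.2 refers to the first dosing date without saying in which study.

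**Population.** Protocol 11.3.1: "The safety analysis set will consist of all subjects who receive at least 1 dose of IMP in the extension study". SAP 3.1.2 (SAFe) matches this, and SAP 5.6 applies SAFe to all safety output. SAP 3.1.2 adds that "data will be presented also using the randomization groups of ADORE study".

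**Who enters.** The protocol's rationale describes patients "who have demonstrated a good tolerance in the ADORE trial (either FAB122 or placebo arm) during 48 weeks and up to 72 weeks". Protocol 5.2 requires completion of ADORE. Protocol 5.3 excludes from extension treatment any "Patient who discontinued study drug prematurely in the double-blind phase of the study (ADORE Study) for safety reasons". Protocol 4 lets patients who stopped ADORE drug for other reasons restart.

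**Format.** SAP 5.6.1 gives numbers of patients, numbers of events and percentages of patients. Protocol 11.3.5 planned to tabulate exposure to study drug. SAP 5.7 puts dosing out of scope, and the table list in SAP 9.3 has no exposure table.

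**Contrast.** For survival, SAP 5.5.2.1 states: "Endpoints will be derived by combining the survival data from ADORE and ADOREXT". No such step is planned for adverse events.

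**The concern.** The primary objective is long-term safety. A patient randomised to FAB122 in ADORE can reach the extension after 48 to 72 weeks on drug, while a patient randomised to placebo has had none. The SAP starts the AE clock at zero for both and shows them in adjacent columns, with no measure of time at risk.

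Two things are at stake. First, no planned output lets a reader see AE frequency by total time on FAB122, which matters for any effect that depends on cumulative dosing; the protocol itself follows potential neurotoxicity. Second, a difference between the ADORE-group columns could be read as a treatment or tolerability signal when it may reflect only prior exposure and selection.

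**Working it through.** The documents state no safety rate, event count or extension follow-up, so there is no figure of the plan's own to reproduce. The check is a trace of what enters the tables, followed by exposure arithmetic with labelled assumptions.

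**1. What the TEAE tables leave out**

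- Former placebo patients: nothing on FAB122. Their first extension dose is their first FAB122 dose.
- Former FAB122 patients: all exposure in ADORE, and AEs that began in ADORE and persist unchanged. An event that worsens gets a new start date under Protocol 9.1.1 and should therefore count.
- Patients who stopped FAB122 in ADORE for safety: absent, because they are not dosed in the extension.

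Two rows of the AE overview (any serious AE, any AE leading to death) are not confined to TEAEs. They still use SAFe, and nothing in the SAP says that ADORE AE records feed them.

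**2. Share of a former FAB122 patient's exposure before time zero**

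Share = prior weeks / (prior weeks + extension weeks). Prior weeks are 48 or 72 (protocol rationale), taking dosing in ADORE as continuous. Extension weeks are not given. For a rough maximum, take the interval from a protocol date to the SAP date, 19 Apr 2024:

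- from the earliest country version in SAP 1 (24 Jan 2023): 451 days / 7 = 64.4 weeks
- from protocol version 1.0 (17 Oct 2022): 550 days / 7 = 78.6 weeks

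| Extension weeks (assumed) | 48 prior weeks | 72 prior weeks |
|---|---|---|
| 12 | 80% | 86% |
| 26 | 48/74 = 65% | 72/98 = 73% |
| 52 | 48% | 58% |
| 64.4 | 48/112.4 = 43% | 72/136.4 = 53% |
| 78.6 | 48/126.6 = 38% | 72/150.6 = 48% |
| 156 (the planned 3 years) | 24% | 32% |

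For former placebo patients the share is 0% throughout.

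**3. Person-time left out**

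Patient-years = N × share randomised to FAB122 × prior weeks / 52.18. N is 200–225 (Protocol 11.2). The ADORE allocation is not in these documents; 1/2 to 2/3 is assumed.

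- Low: 200 × 1/2 × 48 / 52.18 = 92
- High: 225 × 2/3 × 72 / 52.18 = 207

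This takes the planned N as patients dosed in the extension. Earlier stopping of drug would lower it. FAB122 time in ADORE patients who never took extension drug would come on top.

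**4. What the ADORE-group columns can show**

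Hypothetical figures: a 10% background risk over 26 extension weeks, plus a 20% drug-related risk.

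- If the drug risk falls entirely early after first dose: former placebo 1 − 0.90 × 0.80 = 28%; former FAB122 10%.
- If it appears only after long exposure: the same arithmetic gives 10% for former placebo and 28% for former FAB122.

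The drug is the same in both columns. The gap comes from prior exposure alone, and its sign depends on a time pattern that the documents do not supply.

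**5. Selection**

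Both groups had to complete ADORE without stopping drug for safety, but one passed that filter on FAB122 and the other on placebo. The groups in SAFe are therefore no longer the groups that were randomised.

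**The case against.** The strongest reply is that nothing here is wrong. The extension-only rule follows the protocol's safety set, is the usual convention for a stand-alone extension, and is the correct FAB122 time zero for former placebo patients. Events in ADORE belong to ADORE, and its report or an integrated summary may cover cumulative exposure. Leaving out unchanged ongoing events is the ordinary meaning of treatment-emergent. The study ended early and the SAP was deliberately cut back.

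Most of this stands: the definition should stay. Four stronger readings are tempting, and the documents do not support them.

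- *That the SAP compares AEs between randomised arms.* It plans no test, risk difference or hazard ratio for AEs. The columns are descriptive, and splitting by ADORE group at least separates patients with and without prior FAB122.
- *That the SAP removed the intolerant FAB122 patients.* The exclusion is a protocol eligibility rule and applies to both arms.
- *That the former FAB122 column will look better.* Depletion of susceptible patients would push that way and cumulative toxicity the other. Neither is established.
- *That at least half of the exposure is discarded.* Follow-up is not given, and at the longest intervals considered the share can be below half.

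What the reply does not answer is the missing exposure information. Early termination explains a shorter SAP, but safety is the primary objective it retains, and separate reports cannot give rates by time since first FAB122 dose unless someone merges the data. These documents plan no such merge.

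**Conclusion.** The TEAE definition is sound; the gap is that it is the only safety analysis. No planned output relates adverse events to time on FAB122: there is no exposure table, no person-time rate and no count from first FAB122 dose. The ADORE-group columns carry no caveat although they differ in prior exposure and selection.

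The exact size cannot be computed. If extension follow-up was at most about 64–78 weeks, roughly 38–53% of a former FAB122 patient's time on drug precedes the SAP's time zero; at 26 weeks it is 65–73%. Across the planned extension size this is about 92–207 patient-years. These figures assume continuous dosing in ADORE, an allocation share of 1/2 to 2/3, and that document dates bound the follow-up. Patients who stopped ADORE drug and later restarted have less prior exposure.

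This limits how far the report can answer its primary question. It does not invalidate the planned tables.

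**What to change.** Keep the extension-only SAFe tables as planned, and add the following:

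1. **Exposure and rates.** Restore the exposure table from Protocol 11.3.5, and give events per 100 person-years beside the crude percentages.
2. **One supportive table set from first FAB122 dose.** Cover TEAEs, serious TEAEs and TEAEs leading to discontinuation. Time zero is ADORE dose 1 for patients randomised to FAB122 and extension dose 1 for those randomised to placebo. Include every FAB122-treated patient, including those who stopped in ADORE for safety. Give person-time rates by time since first FAB122 dose, for example 0–24, 24–48, 48–72 and over 72 weeks. State how gaps off drug are handled, and that later bands describe only patients still followed on drug.
3. **A footnote** on each table split by ADORE group: the columns are not a randomised comparison and differ in prior FAB122 exposure and selection.

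In the same edit, name the study in the first dosing date of SAP 5.2 and carry the protocol's worsening clause into SAP 5.6.1.

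The cost is merging ADORE AE and dosing data and programming one extra table set. The SAP already combines survival data across the two studies and inherits ADORE datasets for history and randomisation (SAP 5.2). MedDRA versions may need aligning: SAP 8.2 uses the latest version at database lock, and the ADORE version is not stated here.
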